6.2. Stopping Rules for Individual Subjects

Subjects who meet any of the following criteria should be discontinued from the study and complete an Early Termination Visit and return for Post-treatment Follow-up visits:

- Elevation of ALT and/or AST >5x baseline or 5x nadir (unrelated to any interventional procedure)
- Confirmed total bilirubin >3x baseline or 3x nadir with the total bilirubin > 5 mg/dL
 - If total bilirubin > 5mg/dL, bilirubin should be monitored on a weekly basis.
 - If direct bilirubin > 3mg/dL, study drugs should be discontinued.
- Any non-laboratory Grade 4 event assessed as related to treatment with SOF/LDV
- Worsening of disease state as evidenced by progressing hepatic decompensation

The investigator is responsible for reviewing local laboratory results to determine if a stopping rule has been met.

6.3. Criteria for Discontinuation of Study Treatment

Study medication may be discontinued in the following instances:

- Intercurrent illness that would, in the judgment of the investigator, affect assessments of clinical status to a significant degree or create a safety risk for the subject.
- Unacceptable toxicity, as defined in the toxicity management section of the protocol, or toxicity that, in the judgment of the investigator, compromises the ability to continue study-specific procedures or is considered to not be in the subject's best interest
- Subject request to discontinue for any reason
- Subject noncompliance
- Pregnancy or partner pregnancy during the study
- Discontinuation of the study at the request of study sponsor, regulatory agency or an IRB

6.4. Discontinuations

If the subject meets the Virologic Response-Based Criteria (Section 6.6), the Stopping Rules for Individual Subjects (Section 6.7) or other criteria for discontinuation of study treatment (Section 6.8), the subject should complete an Early Termination Visit as soon as possible after all therapy is discontinued. The subject should continue to follow the applicable Post-Treatment visit schedule. Evaluation of stopping rules for each subject will be determined by the Principal Investigator (PI) at the site.

Subjects discontinuing treatment prior to completion of the assigned dosing period for reasons other than those described in Section 6 should complete the assessments for early termination as described in Section 5.2.6.

Subjects with HCV RNA < LLoQ who permanently discontinue all study drugs for any reason including safety and/or tolerability concerns prior to completion of the assigned dosing period should complete the early termination visit and will be followed according to the post-treatment study assessments to determine whether the subject achieves SVR.

6.5. Assessments for Premature Discontinuation from Study

If a subject discontinues medication dosing (for example, as a result of an adverse event [AE]), every attempt should be made to keep the subject in the study and continue to perform the required study-related follow-up and procedures. If this is not possible or acceptable to the subject or investigator, the subject may be withdrawn from the study.

7. ADVERSE EVENTS

7.1. Adverse Events

An adverse event (AE) is any untoward medical occurrence in a clinical investigation subject administered a medicinal product and which does not necessarily have a causal relationship with this treatment. An AE can therefore be any unfavorable and unintended sign, symptom, or disease temporally associated with the use of a medicinal product, whether or not considered related to the medicinal product.

AEs also include the following:

- Pre- or post-treatment complications that occur as a result of protocol mandated procedure (e.g. such as venipuncture, biopsy) during or after screening (before the administration of study medicinal product).
- Any pre-existing condition that increases in severity, or changes in nature during or as a consequence of the study medicinal product phase of a human clinical trial, will also be considered an AE.
- Complications and termination of pregnancy

An AE does not include the following:

- Medical or surgical procedures (e.g., surgery, endoscopy, tooth extraction, transfusion) performed; the condition that leads to the procedure is an adverse event
- Pre-existing diseases or conditions or laboratory abnormalities present or detected before the screening visit that do not worsen
- Situations where an untoward medical occurrence has not occurred (e.g., hospitalization for elective surgery, social and/or convenience admissions)
- Overdose without clinical sequelae
- Any medical condition or clinically significant laboratory abnormality with an onset date before the consent form is signed and not related to a protocol-associated procedure is not an AE. It is considered pre-existing and should be documented on the medical history CRF.
- Uncomplicated pregnancy.
- An induced elective abortion to terminate a pregnancy without medical reason.

Only adverse events that lead to drug discontinuation or withdrawal will be entered into the database.

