Screening assessments include physical examination with height and weight measurements, vital signs, medical history review for eligibility determination, safety laboratory tests, HCV RNA and HCV genotyping, HIV and HBV testing, serum β-hCG (females of childbearing potential only), ECG, and Fibroscan (if needed)

On-treatment assessments include adverse events (AEs) assessments, concomitant medications, physical examination, vital signs, safety laboratory tests, HCV RNA, ECG

Post-treatment assessments include adverse events (AEs) assessments, concomitant medications, physical examination, vital signs, safety laboratory tests, HCV RNA, ECG

Test Product, Dose, and Mode of Administration:

All study subjects will receive the sofosbuvir 400 mg and ledipasvir 90 mg fixed dose combination. Subjects will take one tablet in the morning.

Evaluation criteria Safety

AEs that lead to discontinuation, SAEs and safety laboratory tests will be collected until 4 weeks after the last dose of study drug. Safety endpoints will include

- Completion of full course of therapy
- Discontinuation for adverse events
- Serious adverse events

Efficacy

Efficacy will be evaluated using scheduled assessments of HCV RNA by PCR. All endpoints will be summarized with descriptive

statistics by cohort. Number and percent of subjects in each cohort will be presented for categorical variables. For continuous variables, N, mean, SD, Median, Q1, Q3, minimum and maximum will be presented.

The primary efficacy endpoint will be the SVR12 defined as HCV RNA < LLoQ for 12 weeks post-treatment.

GLOSSARY OF ABBREVIATIONS AND DEFINITION OF TERMS

AE adverse event

ALT alanine aminotransferase AST aspartate aminotransferase

BMI body mass index
BW Body weight
CLcr creatinine clearance

COPD Chronic obstructive pulmonary disease

CRF case report form(s)

dL deciliter

ECG electrocardiogram
e.g. For example
ET Early termination

FDA (United States) Food and Drug Administration

FDC Fix Dosed Combination FEV1 Forced expiratory volume

GCP Good Clinical Practice (Guidelines)

Hb hemoglobin

hCG human chorionic gonadotropin

HBV Hepatitis B virus HCV Hepatitis C virus

HIV Human Immunodeficiency Virus

ICF Informed Consent Form

ICH International Conference on Harmonisation

i.e. for explanation

ILD Interstitial lung disease
INR International normalized ratio
IRB institutional review board

LDV ledipasvir

LLoQ lower limit of Quantification MCV Mean corpuscular volume

mg milligram
mL milliliter

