7.2. Assessment of Adverse Events

All AEs will be assessed by the investigator or qualified designee and only AEs that lead to discontinuation will be recorded on the AE CRF page. The AE entry should indicate whether or not the AE was serious, the start date (AE onset), the stop date (date of AE resolution), whether or not the AE was related to medicinal product, the action taken with medicinal product due to the AE, and the severity of the AE..

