7.3.1. Serious Adverse Event Reporting Requirements

Investigators are to submit a MedWatch 3500 form to FDA on any event that, in the investigator's opinion, is related to the study drug and is unexpected. Send a copy of the MedWatch form to the DCRI.

7.3.2. Clinical Laboratory Abnormalities and Other Abnormal Assessments as Adverse Events or Serious Adverse Events

Laboratory abnormalities are usually not recorded as AEs or SAEs. However, laboratory abnormalities (e.g., clinical chemistry, hematology, and urinalysis) independent of the underlying medical condition that lead to discontinuation must be recorded as an AE, as well as an SAE, if applicable.

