8.1.4. Safety Endpoints

In addition to the primary endpoint of completion of full course of therapy, safety endpoints will include rates of discontinuation for adverse events and serious adverse events. Safety will also be assessed with adverse events and laboratory tests.

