8.6. Safety Analysis

Safety will be evaluated by assessment of clinical laboratory tests, physical examinations, vital signs measurements, at various time points during the study, and by the documentation of AEs. All safety data collected while "on treatment" (i.e., on or after the first dose of study drug administration up to 30 days after the last dose of study drug) will be summarized by treatment arm according to the study drug received.

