8.6.1. Adverse Events

Clinical and laboratory adverse events will be summarized on the basis of the date of onset for the event. A treatment-emergent adverse event will be defined as any adverse event that begins on or after the date of first dose of medicinal product up to the date of last dose of medicinal product plus 30 days.

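### Sections 7.1 and 7.2 keep every adverse event that does not stop treatment out of the database, so the planned SAE rate would be biased low

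*Combined protocol and SAP*

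**What the plan says.** **Collection rules.** Section 7.1 closes with "Only adverse events that lead to drug discontinuation or withdrawal will be entered into the database". Section 7.2 says that "only AEs that lead to discontinuation will be recorded on the AE CRF page" and then that "The AE entry should indicate whether or not the AE was serious". Seriousness is therefore recorded on the restricted entry, and neither section makes an exception for SAEs.

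**Synopsis (Evaluation criteria, Safety).** The collection rule given there is different: "AEs that lead to discontinuation, SAEs and safety laboratory tests will be collected until 4 weeks after the last dose of study drug". The list that follows gives three separate safety endpoints: completion of the full course, discontinuation for adverse events, and serious adverse events.

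**Analysis sections.** Section 8.1.4 says "safety endpoints will include rates of discontinuation for adverse events and serious adverse events" and adds that adverse events and laboratory tests will also be used to assess safety. Section 8.6 covers safety data from first dose "up to 30 days after the last dose of study drug". In 8.6.1, "A treatment-emergent adverse event will be defined as any adverse event that begins on or after the date of first dose of medicinal product", with the same 30-day limit.

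**Other routes for an SAE.** Section 7.3.1 asks for a MedWatch form, copied to the DCRI, only where the investigator judges that the event "is related to the study drug and is unexpected". Section 9.1.6 keeps a record of all adverse events in the site's source documents.

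**The concern.** The primary objective is safety and tolerability in subjects with advanced heart failure or lung disease, and SAEs are one of the named safety endpoints. Section 7.3 defines an SAE by its outcome, such as an in-patient admission, and not by whether study drug was stopped. A subject admitted for heart failure or COPD who stays on treatment has had an SAE, but under 7.1 and 7.2 that event is not entered.

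At stake are two planned outputs. The SAE rate would become the rate of SAEs that led to discontinuation or withdrawal. The treatment-emergent summary would become a table of events leading to discontinuation, without saying so. The documents do not say which text governs. If some sites worked from the synopsis and others from Section 7, the SAE rate would also depend on the site.

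**Working it through.** The plan gives no expected SAE rate and no derivation of the sample size, so there is no figure of its own to reproduce. The check has three parts.

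**1. Does any described route bring a non-discontinuing SAE into the database?**

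| Route | Limit |
|---|---|
| Database entry (7.1) | Event must lead to drug discontinuation or withdrawal |
| AE page (7.2) | Event must lead to discontinuation; seriousness is a field here |
| MedWatch copy (7.3.1) | Event must be judged both related and unexpected; goes to the DCRI, with no stated entry into the database |
| Laboratory abnormality as AE or SAE (7.3.2) | Must lead to discontinuation |
| Source record (9.1.6) | All adverse events, but nothing moves them into the database |

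None does. The case report forms are not part of the documents, so a separate SAE page may exist, but none is described.

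**2. Direction and size of the bias.** Let p be the true share of subjects with an SAE, and f the share of those subjects whose SAE leads to discontinuation or withdrawal. With n subjects:

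- recorded SAE proportion = p × f, which is below p unless f = 1
- expected recorded subjects = n × p × f
- probability of recording none = (1 − p × f)^n

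The cohort size n = 25 is from Section 3.3. Both p and f are assumptions. For p = 20%:

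| f | Recorded proportion | Expected of 25 | Probability of none |
|---|---|---|---|
| 1 | 20% | 5 | 0.80^25 = 0.4% |
| 0.75 | 15% | 3.75 | 0.85^25 = 1.7% |
| 0.5 | 10% | 2.5 | 0.90^25 = 7.2% |
| 0.25 | 5% | 1.25 | 0.95^25 = 27.7% |

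At f = 0.5, other values of p give: p = 10%, recorded 5% (1.25 subjects, probability of none 27.7%); p = 40%, recorded 20% (5 subjects, 0.4%). For all 50 subjects at p = 20%, the expected count falls from 10 to 5 (f = 0.5) or 2.5 (f = 0.25). The plan specifies confidence intervals only for SVR, but a reader who put an exact 95% interval on 0 of 25 would get 0% to 13.7%, which excludes the assumed 20%.

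Part of the loss is built in. In a subject who completes treatment, an SAE starting after the last dose cannot lead to drug discontinuation; only withdrawal from the study could admit it. That period is 30 of 84 + 30 = 114 days (26%) of the treatment-emergent window for 12-week subjects, and 30 of 168 + 30 = 198 days (15%) for 24-week subjects.

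**3. Window.** Collection stops at 4 weeks (28 days) in the synopsis, while analysis runs to 30 days. The gap is 2 days: 2/114 = 1.8% or 2/198 = 1.0% of the window. This is minor.

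**The case against.** The strongest reply is that Section 7.1 merely omits a mention of SAEs. Section 7.3 speaks of documenting a diagnosis as an AE and/or an SAE, and 7.3.2 of recording some laboratory abnormalities as both, which suggests that SAE records are distinct from AE records. On that reading 7.2 governs only the AE page, and the synopsis shows the intention to collect SAEs. This is plausible as to intent, but 7.1 limits the whole database and no SAE route is described, so the text still has to change.

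Second, some SAEs do pass the filter. Section 6.2 calls for discontinuation after certain events, among them related non-laboratory Grade 4 events, specified liver-test elevations and progressing hepatic decompensation. That stands: it raises f. It does not reach SAEs judged unrelated, which in this population are likely to include admissions for the underlying heart or lung disease.

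Third, 8.6.1 defines timing and does not promise complete collection, and restricting non-serious AE collection for a marketed product is a legitimate choice. That also stands. For that table the problem is incompleteness, and an accurate label would cure it. Likewise, 8.1.4 taken alone can be read as meaning discontinuation for AEs and for SAEs; the separate synopsis item points the other way.

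Fourth, the size is illustrative, site differences are only a possibility, and the ±5-day visit allowance exceeds the 2-day window gap. All true. None of these removes the contradiction.

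**Conclusion.** The concern holds. Sections 7.1 and 7.2 cannot both be followed and yield the SAE endpoint in the synopsis. If they are followed, the SAE rate is biased low unless every subject with an SAE discontinues or withdraws because of it, and the treatment-emergent summary is incomplete. The direction rests on the text alone, given that no separate SAE form is described. The size cannot be fixed from the documents: with p = 20% assumed, the recorded rate runs from 5% at f = 0.25 to an unbiased 20% at f = 1. Completion of therapy, discontinuation for adverse events and SVR12 are unaffected. Because safety is the primary objective and this endpoint cannot be validly estimated under Section 7 as written, the text must be corrected.

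**What to change.** - **7.1 and 7.2:** state that all SAEs, regardless of causality, expectedness or effect on study drug, and all AEs leading to discontinuation or withdrawal, will be entered in the database.
- **8.1.4:** list the endpoints separately: (i) discontinuation for adverse events; (ii) any serious adverse event.
- **Synopsis, 8.6 and 8.6.1:** use one safety window, for example collection to 30 days after last dose to match the analysis.
- **8.6.1:** either limit the tables to SAEs plus AEs leading to discontinuation and label them so, or enter all AEs.

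The cost is protocol wording and SAE entry in REDCap for about 50 subjects at 5 sites. Adverse events are already assessed at each visit from Day 1 to post-treatment week 12 (Appendix 1) and kept in source (9.1.6), so no visit or procedure is added. The downside is a modest amount of extra data entry.

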7.2. Assessment of Adverse Events

All AEs will be assessed by the investigator or qualified designee and only AEs that lead to discontinuation will be recorded on the AE CRF page. The AE entry should indicate whether or not the AE was serious, the start date (AE onset), the stop date (date of AE resolution), whether or not the AE was related to medicinal product, the action taken with medicinal product due to the AE, and the severity of the AE..

7.3. Serious Adverse Events

A serious adverse event (SAE) is defined as follows:

Any adverse drug experience occurring at any dose that results in any of the following outcomes:

- Death
- Life-threatening situation (subject is at **immediate** risk of death)
- In-patient hospitalization or prolongation of existing hospitalization (excluding those for study therapy or placement of an indwelling catheter, unless associated with other SAEs)
- Persistent or significant disability/incapacity
- Congenital anomaly/birth defect in the offspring of a subject who received medicinal product
- Other: medically significant events that may not be immediately life-threatening or result in death or hospitalization, but based upon appropriate medical and scientific judgment, may jeopardize the subject or may require medical or surgical intervention to prevent one of the outcomes listed above

Examples of such events are as follows:

- Intensive treatment in an emergency room or at home for allergic bronchospasm
- Blood dyscrasias or convulsions that do not result in hospitalization
- Development of drug dependency or drug abuse

Clarification of Serious Adverse Events

- Death is an outcome of an AE, and not an adverse event in itself. In reports of death due to "Disease Progression," where no other information is provided, the death will be assumed to have resulted from progression of the disease being treated with the medicinal product(s).
- The subject may not have been on medicinal product at the occurrence of the event. Dosing
 may have been given as treatment cycles or interrupted temporarily before the onset of the
 SAE, but may have contributed to the event.
- "Life-threatening" means that the subject was at immediate risk of death from the event as it
 occurred. This does not include an event that might have led to death if it had occurred with
 greater severity.
- Complications that occur during hospitalizations are AEs. If a complication prolongs the hospitalization, it is a SAE.
- "In-patient hospitalization" means the subject has been formally admitted to a hospital for medical reasons, for any length of time. This may or may not be overnight. It does not include presentation and care within an emergency department.
- The investigator should attempt to establish a diagnosis of the event on the basis of signs, symptoms and/or other clinical information. In such cases, the diagnosis should be documented as the AE and/or SAE and not the individual signs/symptoms.

A distinction should be drawn between seriousness and severity of AEs. An AE that is assessed as Grade 4 (potentially life-threatening) should not be confused with an SAE. Severity is a category utilized for rating the intensity of an event; and both AEs and SAEs can be assessed as Grade 4. An event is defined as "serious" when it meets one of the predefined outcomes described above in Section 7.3.

7.3.1. Serious Adverse Event Reporting Requirements

Investigators are to submit a MedWatch 3500 form to FDA on any event that, in the investigator's opinion, is related to the study drug and is unexpected. Send a copy of the MedWatch form to the DCRI.

7.3.2. Clinical Laboratory Abnormalities and Other Abnormal Assessments as Adverse Events or Serious Adverse Events

Laboratory abnormalities are usually not recorded as AEs or SAEs. However, laboratory abnormalities (e.g., clinical chemistry, hematology, and urinalysis) independent of the underlying medical condition that lead to discontinuation must be recorded as an AE, as well as an SAE, if applicable.

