9.3. Study Discontinuation

Both the sponsor and the investigator reserve the right to terminate the study at any time. Should this be necessary, both parties will arrange discontinuation procedures and notify the appropriate regulatory authority and IRBs. In terminating the study, the sponsor and the investigator will assure that adequate consideration is given to the protection of the subjects' interests.

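### A serious adverse event judged unrelated that does not stop the drug has no stated route to the sponsor or the DCRI, no safety report has a deadline, and no cross-site review is described

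*Combined protocol and SAP*

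**What the plan says.** Four parts of the protocol bear on how a serious event leaves a site.

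- **Reporting outside routine data entry.** Section 7.3.1 is the only SAE reporting rule. It calls for a MedWatch form to FDA when the site believes that an event "is related to the study drug and is unexpected. Send a copy of the MedWatch form to the DCRI". The trigger is the site's judgement on both relatedness and expectedness. There is no time limit.
- **Routine data entry.** Section 7.1 states: "Only adverse events that lead to drug discontinuation or withdrawal will be entered into the database". Section 7.2 agrees: "only AEs that lead to discontinuation will be recorded on the AE CRF page". Section 9.1.7 leaves the time for completing REDCap screens after a visit at whatever is reasonable, and requires a reason for any withdrawal. Section 5.3.1 has sites enter laboratory data.
- **What is to be collected and analysed.** The synopsis, under evaluation criteria, says SAEs are collected until 4 weeks after the last dose. Section 8.1.4 lists SAE rates among the safety endpoints.
- **Who decides.** Within a subject, "Evaluation of stopping rules for each subject will be determined by the Principal Investigator (PI) at the site" (6.4). For the whole study, 9.3 says "Both the sponsor and the investigator reserve the right to terminate the study at any time", and 6.3 lists "Discontinuation of the study at the request of study sponsor, regulatory agency or an IRB" among the reasons for ending treatment.

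No medical monitor, safety board, periodic pooled review or study-level stopping rule is described.

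**The concern.** Safety and tolerability is the primary objective (section 2). The subjects have NYHA class III or IV heart failure with a hospitalization in the past year, or ILD or COPD that is severe or oxygen-dependent (section 3.4). Admissions and deaths can plausibly be put down to the underlying disease, one subject at a time. The documents do not say how often that will happen, but any event so judged falls outside 7.3.1.

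There is no control arm, so an excess of cardiac or respiratory events would have to be recognised from the accumulated rate across sites. If the plan is followed as written, some of those events never enter the shared data, the rest arrive with no deadline, and nobody is assigned to add them up. The sponsor's ability to act under 6.3 and 9.3 then depends on information that the protocol does not require anyone to send.

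**Working it through.** **Step 1: trace each kind of event.** The plan states no SAE rate, power or threshold, so there is no figure to reproduce. The sections, taken together, give:

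| Event | Report under 7.3.1 | Database under 7.1, 7.2, 9.1.7 | Deadline |
|---|---|---|---|
| Judged related and unexpected | Yes, FDA with copy to DCRI | Only if it ends drug or participation | None |
| Other SAE that ends drug or participation | No | Yes, with a seriousness flag | None in days |
| Death on treatment, judged unrelated or expected | No | Should be entered, since dosing ends | None in days |
| Death after treatment, judged unrelated or expected | No | Possibly, as a withdrawal reason | None in days |
| Other SAE, drug continues | No | No | Not applicable |

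The last row is the gap. It also conflicts with the synopsis and 8.1.4: a rate of SAEs cannot be tabulated from a database that excludes those that did not stop the drug.

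**Step 2: does pooling matter?** Inputs from the synopsis: 5 sites, about 50 subjects, about 25 per cohort. Assumed: 10 subjects per site, and a background SAE risk p that is truly doubled to 2p. The measure is how surprising the expected doubled count would be if the risk were still p:

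P(X ≥ 2pn), with X ~ Binomial(n, p).

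For p = 0.20:

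| Subjects seen (n) | Count (2pn) | P under background |
|---|---|---|
| 10 (one site, or first 10 pooled) | 4 | 0.121 |
| 20 pooled | 8 | 0.032 |
| 25 (one cohort) | 10 | 0.017 |
| 30 pooled | 12 | 0.0095 |
| 50 pooled | 20 | 0.0009 |

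For one 25-subject cohort, the tail is 0.098 at p = 0.10 (5 or more events) and 0.002 at p = 0.30 (15 or more).

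**Step 3: a check that needs no rate.** Suppose 5 of the 50 subjects have an SAE, spread at random over five sites of 10. The chance that no site has 3 or more is the coefficient of x^5 in (1 + 10x + 45x²)^5, divided by C(50,5):

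(100,000 + 900,000 + 607,500) / 2,118,760 = 1,607,500 / 2,118,760 = 0.76.

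A modest cluster would usually not stand out at any one site.

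**The case against.** The strongest reply is that the sponsor is not blind. Adverse events that end treatment are entered from every site with no causality filter and with seriousness, relatedness and severity recorded (7.2). Withdrawal reasons (9.1.7) and laboratory results (5.3.1) are entered too, and the DCRI and monitors may see source documents (9.1.8, 9.1.10). All of that stands. A reader might infer that the sponsor can never see a cross-site cluster, or is never told of deaths. The documents do not support that: fatal and treatment-ending events should reach REDCap, though with no fixed time and no one named to review them. What is missing is a requirement to tell promptly, not every means of knowing. Source access is a right to look and does not cause a site to send anything.

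Nor does the power to stop the study rest with the sponsor alone. Section 9.3 gives it to the investigator as well. The DCRI's relation to the sponsor is not defined in the text supplied; title pages were removed, so that is not counted as a fault.

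A fair statistical objection is that setting one site against all 50 subjects flatters pooling, because by then enrolment is over. At the first 10 subjects pooling gains nothing (0.121 either way). At a 10% background the pooled tail is still 0.133 at 20 and 0.073 at 30. With no background rate in the documents and no control arm, a reviewer would also have no set reference to test against. These limits are real: they make the review a matter of judgement and its gain gradual. They do not touch the reporting gap.

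Finally, this is an approved, marketed product (1.2, section 4), which may lessen the need for expedited regulatory reports. It does not remove the need to tell the study's own coordinators about SAEs that are an endpoint of the study.

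**Conclusion.** The point holds in this limited form. The protocol requires no timed report of any death or SAE. The one report it requires outside routine entry is filtered by the site's view of relatedness and expectedness. SAEs that do not stop the drug are kept out of the database although they are to be collected and analysed, and no cumulative cross-site review is described. The routing gap and the internal conflict follow from the text alone and rest on no assumption.

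The size is illustrative. It assumes a 20% background risk, a doubling and independent subjects; the comparison with a single site also assumes equal sites. On those terms pooled evidence strengthens from 0.121 at 10 subjects to 0.0095 at 30 and 0.0009 at 50, and a cohort of 25 gives 0.017 (0.098 to 0.002 for backgrounds of 10% to 30%). The change should be made, chiefly for subject safety; the benefit of pooled review is moderate and comes later in enrolment.

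**What to change.** 1. Amend 7.3.1 so that every death and every SAE from first dose to the end of the SAE collection period is sent to the sponsor/DCRI within a fixed short interval of the site becoming aware of it (for example 24 hours), whatever its causality or expectedness. Keep the MedWatch submission for related and unexpected events.
2. Reconcile 7.1 and 7.2 with the synopsis and 8.1.4, so that all SAEs are entered in the database whether or not the drug is stopped.
3. Have the sponsor assign an existing role to review the cumulative SAE and death listing across sites, by cohort, at fixed intervals. The documents name no medical lead; the only sponsor role mentioned is a project leader for study-drug questions (9.2.2), so the assignment has to be written in.

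The cost is protocol wording, a short SAE form or REDCap screen, and reviewer time. No new committee is needed, and no dose or individual stopping rule changes. The downside is more forms, mostly for background events, in about 50 subjects.
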